2.3 Inclusion and exclusion criteria

The trial will be open to patients:

1. With a diagnosis of COPD who have received pulmonary rehabilitation (or in receipt during the recruitment period)
2. Willing to undergo the collection of assessments planned
3. Willing to be randomised to either the intervention or control group
4. Able to attend one of the two groups planned (given the proposed day and time)

Excluded from the trial will be patients who:

1. Are unable to give informed consent
2. Have comorbid conditions that make participation difficult
3. Are unable to travel independently to the venues
4. Are not sufficiently fluent in English to complete the questionnaires employed

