7.4	Patient consent form	40
7.5	Letter to participant GP	51
7.6	Participant personal information questionnaire	52
7.7	MRC breathlessness scale	55
7.8	COPD Assessment Test	56
7.9	PHQ-9	57
7.10	GAD-7	58
7.11	SF-36v2	59
7.12	Service utilisation questionnaire	62
7.13	Checklist to assess the suitability of patient-reported measures	64
7.14	Statistical analysis plan	65
7.15	The Medway Singing and COPD Programme	55

7.16	Interview schedules	68
7.17	Diary for recording of practice of singing at home	71

Lay Summary

Chronic obstructive pulmonary disease (COPD) is a long-term and progressive respiratory disease which negatively affects people's health and wellbeing. The condition deteriorates over time, and there is no cure. However, there is evidence that activities like regular exercise and singing can improve breathlessness and general health and wellbeing.

Previous research has shown positive benefits of singing for respiratory illness, but two recent reviews of the evidence highlights the need for further larger-scale controlled studies with follow-up.

We plan to set up a randomised controlled trial to assess the potential benefits of singing for COPD patients in Medway. A total of 100 patients with moderate to very severe COPD, as assessed by spirometry, will be recruited, assessed and then randomised into two arms of the trial. Half will participate in a singing programme and half will receive usual care. The singing programme will be implemented over 10 ninety minute sessions. The programme will involve breathing exercises and songs which will encourage controlled breathing and progressive extension of the time taken to breathe out.

Participants who are NOT in the singing groups will be offered the opportunity to join a singing group after the final data gathering session.

For all participants, assessments of lung function, breathing patterns and exercise will be gathered before and after ten weeks of weekly singing and then at follow-up after a further three months. Participants will also complete questionnaires about their breathing, quality of life, personal and mental wellbeing and use of medication and health services.

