1.5 Feasibility studies in Medway

Singing for Better Breathing

As a basis for assessing the feasibility of setting up and running a randomised controlled trial in Medway and in association with Medway Community Healthcare Respiratory Team, two 'singing for better breathing' groups were established in Medway in May, 2017. Participants were recruited through visits to pulmonary rehabilitation classes (PR) run by the respiratory team in two community venues. Members of the De Haan Centre spoke about the idea of 'singing for better breathing' and ran taster exercises. Interest levels were high with approximately half of PR participants expressing a willingness to participate in singing groups. Two groups were set up in Gillingham and St. Mary's Island, and of the people expressing interests at PR, approximately half were able to join one of the groups (i.e. 25% of those contacted initially). This suggests that in recruitment for a further study, at least four times the required sample would need to be reached through direct contact.

The two groups ran weekly over three months, and participants were guided through a structured progressive programme of exercises and singing in line with the approach adopted in previous

studies conducted by the De Haan Centre. In addition, participants were given a printed resource and access to video of exercises and singing to support individual practice at home between sessions.

The singing programme was evaluated by [name] as part of her PhD research within the De Haan Centre, and three measures were employed in a simple baseline-follow up design: the COPD Assessment Test (CAT), the Asthma Control Questionnaire (ACQ) and the Warwick Edinburgh Mental Wellbeing Scale (WEMWBS). The table below gives the means on these questionnaires at baseline and after the programme, and show clearly that significant improvements took place on the CAT and WEMWBS with a marginally significant improvement on the Asthma Control Questionnaire.

Scale	Sample	Baseline	Follow-up	t	p
CAT	21	25	20	2.75	0.01
WEMWBS	21	49	55	-2.61	<0.02
ACQ	20	12	10	2.01	<0.10

The results from the CAT questionnaire were especially encouraging, as the improvement of five points on the scale is clearly greater than the established 'minimal clinically important' change score of two points (Kon et al., 2014).

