1.7 Public and patient involvement

Considerable care has been taken in the design of the current study to consult with patients affected by COPD and interested members of the public (including family members of people with COPD), drawing on participants of singing for better breathing groups previously established by the De Haan Centre and which have continued to meet. A member of the research team has a diagnosis of COPD. In addition, people with COPD and other members of the lay public were formally invited to review the protocol in the course of its development. The Trial Management Committee will also include patients affected by COPD and lay members.

Table 1. Research with controls

Reference	Number of participants (intervention vs control)	Intervention	Control	Measures	Findings	Conclusions
Bonilha et al 2009	Randomised 15:15	1 hr weekly singing for 24 weeks. Relaxation, respiratory & vocal exercises then Brazilian folks songs. Enc home practice	Handcraft work 1 hour weekly over 24 weeks. Relaxation exercises. Including home practice	Pulmonary function, SGRQ, QoL and Borg scale	Intervention group showed small improvement in maximal expiratory pressure, control group declined. Both groups increased their scores on SGRQ	Regular singing may improve QoL and improve maximal expiratory pressure. Additional studies recommended to define role of singing as potential to assist PR
Lord et al 2010	Randomised 15:13	1 hr sessions for 6 weeks of twice weekly singing.	Usual care	SF36, HADS, single breath counting, breath hold, walk test	Significant improvements in anxiety (HADS) and physical component of SF36 in intervention group	Singing classes can improve QoL and anxiety but did not improve measures of breath control or functional capacity. Further work needed to quantify magnitude and duration of improvement
Lord et al 2012	Randomised 13:11	1 hr sessions twice weekly for 8 weeks. Includes vocal exercises, posture and relaxation training. Homework CD.	Weekly Film club for 8 weeks followed by group discussion	HADS, CAT, SF36, walk test, Borg scale, single breath holding	Significant improvements in the physical component of SF36 in intervention group.	Participation in singing lessons may be a useful activity for people with COPD

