The SF-36 will also be used as this measure was employed in both Brompton studies (Lord et al., 2010, 2012), and revealed significant changes on the physical health related quality of life scale, with a large effect of approximately 1. The current study will employ the current version 2 of the SF-36 as opposed to the earlier version used in the previous Brompton studies. This is justified as V2 is the most recent version and we will have the benefit of technical support from Optum, the owners of the scale, together with access to the most recently available and appropriate norms for scoring. We assume that scores arising from the earlier and current version would be virtually identical.

The MRC breathlessness scale (nMRC, see Williams, 2017) will be employed as a score of 3 (out of a score range of 0-4) is often used as a criterion for recommending pulmonary rehabilitation (PR). As this trial will target recruitment towards patients who have undergone or who are receiving PR, it is expected that all participants will have an nMRC score of 3 or 4.

Details of spirometry, SLP assessments and the 6MWT parameters are given in section 2.6 below

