7.6 Participant personal information questionnaire

Participant personal information questionnaire

Name _____

Age _____

Address

Name and address of your GP _____

1. What is your sex? Please circle: Male Female

2. What is your marital status? Please circle:

Single/Unmarried

Married

Same-sex civil partnership

Separated but still legally married or legally in civil partnership

Divorced

Widow/widower (including from civil partnerships)

3. How would you describe your national identity? Please circle:

British

English

Northern Irish

Scottish

Welsh

Another Nationality – Please describe here: _____

4. What is your ethnic group?

Choose one section from A to E, then circle one to best describe your ethnic group or background

A. White

English/Welsh/Scottish/Northern Irish/British

Irish

Gypsy or Irish Traveller

Another white background

B. Mixed/multiple ethnic groups

White and Black Caribbean

White and Black African

White and Asian

Another mixed/multiple ethnic group

C. Asian/Asian British

Indian

Pakistani

Bangladeshi

Chinese

Another Asian background

D. Black/African/Caribbean/ Black British

African

Caribbean

Another Black/African/Caribbean/ Black British

E. Another ethnic group

Arab

Another ethnic background

5. Have you received a formal diagnosis of COPD? Yes No

**6. Have you undertaken pulmonary rehabilitation
in the last THREE months?** Yes No

7. If yes, how many sessions did you attend? _____ sessions

8. How would you describe your level of COPD currently?

Mild

Moderate

Severe

Very severe

**9. Have you experienced any significant worsening
of your COPD over the last THREE months?** Yes No

10. Are you affected by other health conditions? Yes No

9. If yes, please describe here:

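### Section 2.3 omits the spirometric severity range that the lay summary gives for the population, and does not exclude current members of singing-for-breathing groups

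*Protocol*

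**What the plan says.** **Severity.** The Lay Summary states: "A total of 100 patients with moderate to very severe COPD, as assessed by spirometry, will be recruited". Section 2.3 is the list by which patients are admitted. Its only disease criterion is "With a diagnosis of COPD who have received pulmonary rehabilitation (or in receipt during the recruitment period". The other three inclusion criteria concern willingness to be assessed, willingness to be randomised, and ability to attend. The four exclusions concern consent, comorbidity, travel and language (the last being "Are not sufficiently fluent in English to complete the questionnaires employed"). None mentions severity or spirometry.

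Section 2.1 adds that "it is expected that all participants will have an nMRC score of 3 or 4", which is an expectation and not a criterion. Section 2.6 lists FEV1 and FVC among the baseline measurements. The form in 7.6 asks "How would you describe your level of COPD currently" and offers mild as an answer. Section 2.7 stratifies randomisation by sex and COPD severity without saying where the severity grade comes from.

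**Singing.** Section 1.5 says of the 2017 Medway singing groups: "Participants were recruited through visits to pulmonary rehabilitation classes (PR) run by the respiratory team in two community venues". Section 2.2 draws the trial's participants from the same respiratory service's past and current rehabilitation patients. Section 1.7 says of the research centre's earlier groups that they are ones "which have continued to meet". Nothing in 2.3 refers to past or current singing, and neither 7.6 nor 7.12 asks about it.

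**The concern.** Eligibility has to be fixed in the protocol, so both matters belong there.

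On severity, anyone applying 2.3 faithfully may enrol a patient whom the Lay Summary places outside the trial. The population reported at the end could then differ from the one announced. The severity stratum is also undefined: a self-rating and a spirometric grade are both collected and may disagree for the same person.

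On singing, the trial compares singing added to usual treatment with usual treatment alone, and controls are offered singing only after the last assessment (section 3.5). A member of an existing group who has COPD meets 2.3 and could be allocated to control while still singing, or to an intervention already received. Either way the difference between arms shrinks. Because the forms do not ask about singing, this could be neither seen nor described afterwards.

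**Working it through.** **Severity: the texts side by side**

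| Place | What it provides | Entry rule? |
|---|---|---|
| Lay Summary | moderate to very severe, by spirometry | stated population only |
| 1.1 | diagnosis rests on history, examination and spirometry | no, background |
| 2.1 | nMRC 3 or 4 expected | no, expectation |
| 2.3 | COPD diagnosis plus past or current rehabilitation | yes, with no severity limit |
| 2.6 | FEV1 and FVC at baseline | no, measurement |
| 7.6 | self-rated severity, mild allowed | no, questionnaire item |

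The only text that acts as a rule lacks the restriction that the Lay Summary announces. The timetable in 4.1 puts baseline assessments in July and randomisation in August 2019, so spirometry would be available before allocation.

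**Singing: what dilution would cost**

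Inputs:
- Expected effect: 5 CAT points, d about 0.5 (section 2.2), which implies an SD of about 10.
- 40 per arm analysed, two-sided 5%, 90% power claimed (section 2.2).
- 100 recruited, 50 per arm: 80 / (1 − 0.20) = 100, which agrees with the plan.
- Yield from people contacted: about 25% (section 1.5).
- Feasibility participants with CAT data: 21 (section 1.5). This is the only available count of such people.
- Not stated, so assumed: how many existing singers would enrol, and the correlation between baseline and follow-up CAT.

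*The plan's own figure.* With 40 per arm and d = 0.5, a two-sample t-test has power of .60 (.61 by the normal approximation). Reaching 90% needs a baseline-to-follow-up correlation of about .76 for change scores or .72 for ANCOVA; the protocol gives neither. I therefore show dilution on two bases: unpaired, and calibrated so that undiluted power equals the stated 90%.

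*Dilution formula.* If k of 50 per arm are existing singers with no incremental effect, d = 0.5 × (1 − k/50). The two routes give this same factor but do not add. On raw follow-up scores, singing controls already carry the benefit. On change scores, it is the existing singers in the singing arm who show no further gain.

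*Plausible k.* At the protocol's own yield, 0.25 × 21 = 5.25, so about 5 people, or 2 to 3 per arm (about 5%). For k = 5, about 10 of the 21 must enrol. For k = 10, about 20 of the 21 must enrol.

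| k per arm | Share | CAT points | d | Power, unpaired | Power, calibrated to 90% |
|---|---|---|---|---|---|
| 0 | 0% | 5.00 | .500 | .60 | 90% |
| 2 to 3 | 5% | 4.75 | .475 | about .55 | about 87% |
| 5 | 10% | 4.50 | .450 | .51 | about 83% |
| 10 | 20% | 4.00 | .400 | .42 | about 74% |

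The calibrated column scales the standardised effect for 90% power, 1.960 + 1.282 = 3.242, by (1 − share). For example, at 10%: 0.90 × 3.242 = 2.918; 2.918 − 1.960 = 0.958; power about 83%.

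**The case against.** The case on the other side has real weight.

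- **Mild disease is unlikely.** Recruits come from a respiratory service, have had or are having rehabilitation, and are expected to score nMRC 3 or 4. This stands as a reason to expect few such patients, but it is not a rule. A reader might infer that mild patients would dilute the effect. The documents give no figure from which that could be shown, so for them the point is the mismatch in population.
- **The stratum.** A reader might infer that severity for randomisation comes from the self-rating in 7.6. Section 2.7 does not say so, and baseline spirometry is an equally available source. The fault is only that the source is not given.
- **Controls are told they will not sing.** The recruitment text in 7.2 says the comparison half will not be involved in singing, and 2.3 requires willingness to be allocated to either arm. This may deter current singers, but it is not an exclusion. The consent pages are not in the public text, so nothing can be inferred from them.
- **Whether the Medway groups will be singing during the trial.** The remark in 1.7 covers the centre's earlier groups in general, and such projects also ran elsewhere. Section 1.5 shows a Medway group in April 2018. Nothing shows its members singing from September 2019 to March 2020.
- **Size.** A fall in power to .42 should not be read as the expected loss. It needs about 20 of 21 feasibility participants to enrol, against a yield of about a quarter. The low starting value of .60 is a separate sample-size matter.
- **Direction.** Randomisation spreads existing singers over both arms. The result is attenuation, not a bias in favour of singing.

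**Conclusion.** The point holds in two parts. First, section 2.3 contradicts the Lay Summary on severity and spirometric confirmation, and no other section supplies the missing rule. This is a matter of text and rests on no assumption.

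Second, 2.3 leaves the trial open to current members of singing-for-breathing groups from the same recruitment source, and the forms would not reveal them. The loss depends on how many enrol, which the protocol does not state. At the protocol's own yield it is small: about 5 points of power unpaired, or about 3 points from the stated 90%. It reaches 16 to 18 points only near the worst case. These figures assume that all the existing singers have COPD and that each contributes no incremental effect. The gap is worth closing because section 2.2 itself acknowledges concern about being under-powered and the remedy is cheap.

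**What to change.** 1. Reconcile 2.3 with the Lay Summary. Either put the stated severity range into 2.3, checked on the spirometry taken at baseline before randomisation, or correct the stated population to match 2.3.
2. State in 2.7 that the severity stratum is taken from that same baseline spirometry.
3. Add to 2.3 an exclusion for current or recent membership of a singing-for-breathing group, and define the look-back period for recent. An exclusion for any past membership, however distant, would go further than the evidence requires.
4. Add a question on group singing to the baseline form, and record any singing by controls at both follow-up assessments.

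The cost is amendment wording and one or two questionnaire items, with no extra visit. The recruitment pool loses up to about 21 people. If the severity range becomes a criterion, a few people will fail screening at baseline.

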Currently, 115,000 people are newly diagnosed annually and it is the second biggest cause of death in the UK, with approximately 30,000 deaths due to the condition every year.

COPD makes a big impact on hospital services, and currently accounts annually for over 140,000 hospital admissions and over a million bed days across the UK. This is 1.7% of all hospital admissions and bed days. Exacerbation of COPD is the most common cause of readmissions to hospitals in the UK (Royal College of Physicians, 2017). The direct cost of COPD to the UK National Health Service has been estimated at £810-930 million per year and these costs are expected to rise (DH, 2010). Up to 40% of people with COPD are forced to retire from work prematurely because of the disease (Fletcher et al, 2011).

Since smoking remains the primary cause of COPD, smoking cessation is the intervention with the greatest capacity to influence the natural history of the disease (GOLD, 2017). COPD is not curable, however progress may be slowed down and symptoms reduced through pharmacological management using a stepped approach to inhaled therapies (bronchodilators, steroids and combination therapies), based on the severity of the disease (DH, 2010). In addition, pulmonary rehabilitation can significantly improve exercise capacity, dyspnoea and psychological wellbeing and a minimum of 12 supervised sessions is recommended with patients being encouraged to continue exercise beyond the programme (BTS, 2013).

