- SF-36 v2, Physical health related quality of life and Mental health related quality of life (Jenkinson et al., 1999) (Available from Optum: <http://campaign.optum.com/optum-outcomes/what-we-do/health-surveys/sf-36v2-health-survey.html>)
- Generalised anxiety disorder (as assessed by GAD-7) (Spitzer, et al., 2006)
- Depression (as assessed by PHQ-9) (Kroenke, et al., 2001)
- Anxiety (as assessed by GAD-7) (Kroenke, et al., 2002)
- Lung function and patterns of breathing (as assessed by spirometry and SLP – for further details see below)
Functional exercise (as measured by the 6MWT – further details below)
Use of inhalers, consultations with health professionals and hospital admissions

The standardised measures employed in this trial have been chosen based on previous research on singing and COPD, the outcome of recent systematic reviews (Lewis et al., 2016; McNamara et al., 2017, and the latest guidance on the assessment and diagnosis of COPD (NICE, 2018). All questionnaires have been screened and assessed for suitability as ‘patient reported outcome’ measures using the checklist devised by Francis et al. (2016) (see Appendix 7.10).

We are using CAT, GAD-7 and PHQ-9 as these measures are routinely used by the Medway Community Healthcare Respiratory team in the monitoring of responses to pulmonary rehabilitation.

CAT serves as a COPD-specific quality of life measure and is especially suited to being the primary outcome measure for the study. There is also an established ‘minimum clinically importance’ change score of two points (Kon et al., 2014), and this will provide an important criterion against which to judge the outcome of the trial for clinical purposes.

Both GAD-7 and PHQ-9 have established cut-off points for increasing grades of severity on mental health condition, and will serve to assess the extent to which participants in the trial can be regarded as experiencing clinically significant levels of mental health challenge, and whether this changes over the course of the trial for the intervention group relative to the control. It is recognised also that the two mental health scales can be combined to form a single measure of anxiety-depression.

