2.2 Participants

In this study, the participant population will come from the population of COPD patients supported by the Respiratory Service of Medway Community Healthcare. Participants will be recruited from patients who have received PR and those who are currently undergoing PR. The study will seek to achieve a final sample of 80 patients at the second follow-up – 40 in the intervention arm and 40 in the control arm. The intention is to recruit 100 patients who consent to allow for 20% attrition. It is expected that we will need to secure initial expressions of interest from at least 120 people to allow for drop out even prior to consenting.

The number of participants is based on the resources available to run the trial, and no formal power calculation has been used to determine the sample size to be recruited. There is an important ethical issue raised by running a trial that is potentially under-powered. As Freedman et al. (2001:401) put it:

Sample size and power must be addressed before the start of a randomised, controlled trial. It is necessary to know in advance the likelihood of finding valid conclusions from the population assessed. It may be acceptable to subject a patient to a chance of a less than ideal treatment, or to the psychological stress of being a 'subject', if there is a chance of a valid scientific outcome, but it is not ethical to conduct a study the design of which cannot make valid conclusions.

However, relevant considerations are:

- There is no reason to think that participation in the trial will pose any risks to the participants, nor subject them to 'less than ideal treatment' or undue psychological stress. All of our experience with running previous studies in East Kent and Lambeth and Southwark, and the feasibility study in Medway is that participants will find the singing intervention enjoyable and personally and socially beneficial.
-
- The Brompton trials (Lord, 2010, 2012), involved 28 and 24 participants respectively, and reported significant changes in the physical component of the SF-36. The proposed study will be three times larger.
-

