2.5 Intervention and control

Following baseline assessments, participants will be randomly allocated to the control arm, which will be treatment as usual (TAU) following PR, or the intervention group, which will be TAU plus group singing.

There will be two intervention groups in the same community venue in the Medway district meeting on different days. Each group will consist initially of approximately 25 participants at the outset. The groups will be conducted by two experienced and skilled singing facilitators who are trained in facilitating breathing and singing techniques specifically for people with a respiratory disease. A total of 10 sessions will occur over the period of the study, with the expectation that most participants will attend a minimum of 5 sessions. Each session will be run for 90 mins with breathing exercises and singing occurring for one hour. The additional time will allow for the groups to socialise. Details of the programme are given in Appendix 7.12 together with a goals framework with details the links between activities and expected outcomes.

To complement the group singing, intervention participants will also be expected to practise the taught techniques away from the group. This home practice will be supported by a guide and video resources developed specifically for people with COPD. Choir facilitators will encourage use of the resources each week and ask participants to keep a diary of their use of the home programme.

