2.7 Randomisation

Following the assessments of the total sample at baseline, randomisation will be undertaken immediately, with stratification by sex and severity of COPD, and participants informed of their allocation. Use will be made of the 'Sealed Envelopes' professional randomisation service:

<https://www.sealedenvelope.com/>

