4.1 Monthly activities on the project

- June onwards 2018 – Formulate study protocol & develop database
- October 2018 onwards – pre-recruitment publicity – target 120 expressions of interest, with the aim of 100 participants formally consenting.
- December 2018 – Ethics application submitted
- March 2019 – Ethics approved
- April 2019-June 2019 – Recruitment to project
- May-June 2019 – Taster sessions
- July 2019 – Consenting and baseline assessments
- August 2019 – Randomisation and letters to participants
- September - November 2019 – Ten weeks singing intervention
- November - December 2019 – Post-intervention assessments
- December - February 2020 – Post-intervention period
- February - March 2020 – Follow-up assessments and interviews
- April - May 2020 – Data analysis
- May - July 2020 – Writing of papers for peer-reviewed journals
- July 2020 – Publication/Dissemination

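### Patients still in pulmonary rehabilitation can enter and have baseline taken mid-course, although the comparator is defined as care after rehabilitation; the planned within-arm Time tests are exposed, the randomised CAT contrast only slightly

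*Protocol*

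**What the plan says.** Section 2.2 of the protocol states: "Participants will be recruited from patients who have received PR and those who are currently undergoing PR". Section 2.3 repeats this as an inclusion criterion, taking patients "who have received pulmonary rehabilitation (or in receipt during the recruitment period". No section requires the course to be finished before baseline or limits PR afterwards.

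Section 2.5 describes the control arm as care "which will be treatment as usual (TAU) following PR", and the intervention as the same care plus singing. The recruitment text in Appendix 7.2 likewise asks whether the reader has already taken part in PR.

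The calendar in section 4.1 has "April 2019-June 2019 – Recruitment to project" and then "July 2019 – Consenting and baseline assessments". Randomisation is in August, singing starts on 2 September, and the two later assessments (T2 and T3) are in November-December and February-March.

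On the effect of PR, section 1.1 says that "pulmonary rehabilitation can significantly improve exercise capacity, dyspnoea and psychological wellbeing and a minimum of 12 supervised sessions is recommended". Section 2.1 says that CAT, GAD-7 and PHQ-9 are "routinely used by the Medway Community Healthcare Respiratory team in the monitoring of responses to pulmonary rehabilitation".

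Randomisation in section 2.7 is "with stratification by sex and severity of COPD". PR attendance is collected (section 2.6; Appendix 7.6 items 6-7; Appendix 7.12 item 8), but PR status is neither a stratification factor nor a term in the stated 3 by 2 ANOVA. Appendix 7.14 lists tests of Time within each arm, expecting significance under singing and non-significance under usual care.

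**The concern.** For a patient still in PR, the comparator in section 2.5 is not the care delivered, at least for part of the time between baseline and T2. If the July baseline falls inside the course, the change from T1 to T2 contains the rest of the PR response, and the change from T2 to T3 may contain some loss of it. This applies to both arms.

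Two readings of the results are at stake. Improvement over time among singers could be taken as an effect of singing when part of it is PR. A time trend in the usual-care arm could contradict the plan's expectation of no change there for a reason unrelated to the trial. The randomised CAT comparison is touched only through chance imbalance and added noise.

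**Working it through.** No figure in the plan is disputed here. The check asks whether a mid-course baseline can occur, and how much it could matter.

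**Timing.** The protocol gives a minimum of 12 sessions but no frequency; assume one or two a week, so the last session falls 11 or 5 weeks after the first.
- Start in the week of 3 June: last session in the week of 8 July (two a week) or 19 August (one a week).
- Start in the week of 24 June: last session in the week of 29 July or 9 September.
- Start in the week of 1 April: last session in the week of 17 June at the latest, before any baseline.

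Baselines are in the weeks of 1-22 July. A mid-course baseline is therefore possible for late starters and does not arise for the earliest ones. Overlap with singing needs one session a week and a start in the week of 17 June or later.

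**Inputs for size.**
- Completers per arm: 100 recruited less 20% gives 80, so n = 40 (section 2.2).
- SD of CAT: section 2.2 equates 5 points with an effect size of about 0.5, so SD = 5/0.5 = 10.
- Share affected p = 0.3 to 0.5, and PR effect on CAT change D = 2 to 4 points. Both are assumptions.
- Minimal important change on CAT: 2 points (section 2.1).

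**Between-arm contrast.** The expected imbalance is zero. The SD of the chance difference in proportions is √(2p(1−p)/n):
- p = 0.3: √(0.42/40) = 0.102
- p = 0.5: √(0.50/40) = 0.112

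Multiplied by D, the SD of the chance shift runs from 0.102 × 2 = 0.20 to 0.112 × 4 = 0.45 points. The 95% limit, 1.96 × SD × D, runs from 0.40 to 0.88 points.

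The standard error of the arm difference is 10 × √(2/40) = 2.24 points. Variance inflation, p(1−p)D²/SD², runs from 0.21 × 4/100 = 0.8% to 0.25 × 16/100 = 4%. With wider inputs (p from 10% to 50%, D from 2 to 5) it is 0.4% to 6%, and power for a 5-point difference in a two-sided two-sample t-test at 0.05 falls from 0.60 to 0.57 at worst.

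**Within-arm change.** The mean change in each arm due to PR alone is p × D: from 0.3 × 2 = 0.6 to 0.5 × 4 = 2.0 points. The upper end equals the minimal important change. It does not average to zero, because it has the same sign in both arms.

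**Can the recorded items identify it?** Both PR items ask about the last three months. From the last baseline week (22 July) to the first T2 week (11 November) is 16 weeks; from 1 July to 9 December is 23 weeks. Three months is about 13 weeks, so roughly 3 to 10 weeks just after baseline fall outside the T2 recall window, and that is when the rest of a course would be attended. At baseline, item 6 of Appendix 7.6 reaches back to April, but a yes/no answer does not separate an ongoing course from a completed one.

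**The case against.** The strongest reply is that randomisation deals with this. Allocation follows baseline, so PR phase is balanced in expectation, and any chance imbalance is ordinary error already covered by the standard error of the comparison. That stands. A reader might infer that ongoing PR confounds the primary comparison because it is not a stratification factor; the design does not support this. Set against a standard error of 2.24 points, a chance shift with an SD of 0.20-0.45 is small.

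It can also be said that section 2.8 rests inference on comparing the arms at follow-up, and that Appendix 7.14 marks the overall Time effect as not relevant. That stands too, and limits the damage to the subsidiary within-arm tests. Those tests are nevertheless planned, with stated expectations.

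The documents do not state a PR effect on CAT, so calling PR a treatment known to move the primary outcome goes too far. Sections 1.1 and 2.1 together make it an expectation. Nor do they establish that baselines will fall mid-course, since course length and session frequency are not given.

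Broad entry by PR status is a deliberate recruitment choice in a pilot, and PR attendance is recorded. Recording it, and checking baseline equivalence as section 2.8 plans, is not adjustment.

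**Conclusion.** The point holds in a limited form. Sections 2.2 and 2.3 do not fit section 2.5 and must be reconciled. The between-arm CAT contrast remains unbiased, with a chance shift of at most about 0.4-0.9 points at the 95% limit and little loss of power. The within-arm Time tests cannot be read as an effect of singing or as stability under usual care, because PR alone could contribute a mean change of 0.6-2.0 points in each arm.

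All these sizes rest on the assumed share of 30-50% and effect of 2-4 points; the first two also use n = 40, and the power figure the SD of 10 implied by section 2.2.

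A reader might extend the point to the five-point CAT gain in the feasibility groups, who were recruited through PR classes (section 1.5). The documents do not say how many of them were still in PR, so that gain cannot be attributed to it.

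**What to change.** 1. Reconcile sections 2.2 and 2.3 with section 2.5, so that the comparator described is the one that eligible patients receive.
2. Add recent PR at baseline (Appendix 7.6 item 6) as a covariate in the between-arm CAT comparisons at T2 and T3. In the mixed ANOVA it must be allowed to interact with Time, since it is change that PR may affect. Optionally, add it as a stratification factor.
3. Record at baseline whether PR is ongoing or completed, and its end date.
4. Report PR attended during follow-up by arm, noting the three-month recall limit of Appendix 7.12 item 8.
5. State that conclusions rest on the between-arm contrasts, and treat the within-arm Time tests in Appendix 7.14 as descriptive.

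The cost is one degree of freedom in each follow-up comparison, one extra questionnaire item and some rewording.

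Moving baselines into August, or not randomising patients whose PR runs late, is a trade-off for the sponsor and not a required change. Section 2.7 randomises only after the whole sample has been assessed, so later baselines would delay allocation for everyone, and exclusions would cost recruits.
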